#### 16.2.5.3. Listing Conventions

- Listings will be sorted for presentation in order of treatment groups as above, subject number, visit/collection day, and visit/collection time.
- Missing data will be represented on subject listings as either a hyphen ('-') with a corresponding footnote ('- = unknown or not evaluated'), or as 'N/A', with the footnote 'N/A = not applicable', whichever is appropriate.
- Dates will be printed in SAS DATE9.format ('DD\_MMM\_YYYY': 01JUL2000). Missing portions of dates will be represented on subject listings as dashes (--JUL2000). Dates that are missing because they are not applicable for the subject will be output as 'N/A', unless otherwise specified.
- All observed time values will be presented using a 24-hour clock HH:MM or HH:MM:SS format (e.g., 11:26:45, or 11:26). Time will only be reported if it was measured as part of the study.
- Units will be included where available.

#### 16.2.5.4. Figure Conventions

- Unless otherwise specified, for all figures, study visits will be displayed on the X-axis and endpoint (e.g., treatment mean change from baseline) values will be displayed on the Y-axis.

#### 16.2.6. Footnotes

- A solid line spanning the margins will separate the body of the data display from the footnotes.

This document is confidential.

- All footnotes will be left justified with single-line spacing immediately below the solid line underneath the data display.
- Footnotes will always begin with 'Note:' if an informational footnote, or 1, 2, 3, etc. if a reference footnote. Each new footnote will start on a new line, where possible.
- Subject specific footnotes are avoided, where possible.
- Footnotes will be used sparingly and add value to the TFL. If more than six lines of footnotes are planned, then a cover page is strongly recommended to be used to display footnotes, and only those essential to comprehension of the data will be repeated on each page.
- The last line of the footnote section will be a standard source line that indicates the name of the program used to produce the data display, the date the program was run, and the listing source (i.e., 'Program : myprogram.sas Listing source: 16.x.y.z').
- Sources and/or cross-references in footnotes will use the keyword prefix (Listing or Table) for each type of reference and will be separated by a comma when multiple cross-references of the same type are displayed where the prefix will be displayed in plural forms. When multiple types of references are involved, they would be separated by ";".

Example

Listing source: Table 14.2.4.1; Listings 16.2.4.1.1, 16.2.4.1.2, 16.2.4.2.1

This document is confidential.

## 17. Quality Control

SAS programs are developed to produce output such as analysis data sets, summary tables, data listings, figures or statistical analyses. An overview of the development of programs is detailed in **PPD** **Developing Statistical Programs SOP (3907)**.

**PPD** **Developing Statistical Programs SOP (3907)**, **Conducting the Transfer of Biostatistical Deliverables SOP (3908)** and the **SAS Programming and Validation Plan** describes the quality control procedures that are performed for all SAS programs and output. Quality control is defined here as the operational techniques and activities undertaken to verify that the SAS programs produce the output by checking for their logic, efficiency and commenting and by review of the produced output.

This document is confidential.

## 18. Index of Tables

Table Number	Name	Analysis Set
14.1.1.1	Number of Subjects Enrolled and Study Termination	(Screened/Randomized Set)
14.1.2.1	Major Protocol Deviations	(Randomized Set)
14.1.2.2	Reasons for Exclusions from Analysis Sets	(Randomized Set)
14.1.3.1.1	Subject Demographic and Baseline Characteristics	(Randomized Set)
14.1.3.1.2	Subject Demographic and Baseline Characteristics	(Safety Analysis Set)
14.1.3.1.3	Subject Demographic and Baseline Characteristics	(Full Analysis Set)
14.1.3.1.4	Subject Demographic and Baseline Characteristics	(Per Protocol Set)
14.1.3.2.1	Baseline Disease Characteristics	(Randomized Set)
14.1.3.2.2	Baseline Disease Characteristics	(Safety Analysis Set)
14.1.3.2.3	Baseline Disease Characteristics	(Full Analysis Set)
14.1.3.2.4	Baseline Disease Characteristics	(Per Protocol Set)
14.1.3.3	Medical History	(Safety Analysis Set)
14.1.4.1.1	Prior Medications	(Safety Analysis Set)
14.1.4.1.2	Concomitant Medications	(Safety Analysis Set)
14.1.4.2.1	Prior Medical/Surgical Procedures	(Safety Analysis Set)
14.1.4.2.2	Concomitant Medical/Surgical Procedures	(Safety Analysis Set)
14.1.4.3	Prior Biologics or Systemic Treatment for Psoriasis	(Safety Analysis Set)
14.1.5	Extent of Exposure	(Safety Analysis Set)
14.1.6	Treatment Compliance	(Safety Analysis Set)
14.2.1.1.1.1	Proportion of Subjects Achieving PASI-75 at Week 16, Complete Case Analysis	(Full Analysis Set)
14.2.1.1.1.2	Proportion of Subjects Achieving PASI-75 at Week 16 Stratified by Receipt of Any Biologics for Psoriasis, Complete Case Analysis	(Full Analysis Set)
14.2.1.1.2.1	Proportion of Subjects Achieving PASI-75 at Week 16, LOCF	(Full Analysis Set)
14.2.1.1.2.2	Proportion of Subjects Achieving PASI-75 at Week 16 Stratified by Receipt of Any Biologics for Psoriasis, LOCF	(Full Analysis Set)
14.2.1.1.3.1	Proportion of Subjects Achieving PASI-75 at Week 16, NRI	(Full Analysis Set)
14.2.1.1.3.2	Proportion of Subjects Achieving PASI-75 at Week 16 Stratified by Receipt of Any Biologics for Psoriasis, NRI	(Full Analysis Set)
14.2.1.2.1.1	Proportion of Subjects Achieving PASI-75 at Week 16, Complete Case Analysis	(Per Protocol Set)
14.2.1.2.1.2	Proportion of Subjects Achieving PASI-75 at Week 16 Stratified by Receipt of Any Biologics for Psoriasis	(Per Protocol Set)
14.2.1.2.2.1	Proportion of Subjects Achieving PASI-75 at Week 16, LOCF	(Per Protocol Set)
14.2.1.2.2.2	Proportion of Subjects Achieving PASI-75 at Week 16 Stratified by Receipt of Any Biologics for Psoriasis, LOCF	(Per Protocol Set)

This document is confidential.

Table Number	Name	Analysis Set
14.2.1.2.3.1	Proportion of Subjects Achieving PASI-75 at Week 16, NRI	(Per Protocol Set)
14.2.1.2.3.2	Proportion of Subjects Achieving PASI-75 at Week 16 Stratified by Receipt of Any Biologics for Psoriasis, NRI	(Per Protocol Set)
14.2.2.1.1.1	Summary of PASI by Visit: Actual Values, Percent Changes, Proportions of Subjects Achieving PASI-50, PASI-75, PASI-90 and PASI-100, Complete Case Analysis	(Full Analysis Set)
14.2.2.1.1.2	Summary of PASI by Visit: Actual Values, Percent Changes, Proportions of Subjects Achieving PASI-50, PASI-75, PASI-90 and PASI-100 Stratified by Receipt of Any Biologics for Psoriasis, Complete Case Analysis	(Full Analysis Set)
14.2.2.1.2.1	Summary of PASI by Visit: Actual Values, Percent Changes, Proportions of Subjects Achieving PASI-50, PASI-75, PASI-90 and PASI-100, LOCF	(Full Analysis Set)
14.2.2.1.2.2	Summary of PASI by Visit: Actual Values, Percent Changes, Proportions of Subjects Achieving PASI-50, PASI-75, PASI-90 and PASI-100 Stratified by Receipt of Any Biologics for Psoriasis, LOCF	(Full Analysis Set)
14.2.2.1.3.1	Summary of PASI by Visit: Proportions of Subjects Achieving PASI-50, PASI-75, PASI-90 and PASI-100, NRI	(Full Analysis Set)
14.2.2.1.3.2	Summary of PASI by Visit: Proportions of Subjects Achieving PASI-50, PASI-75, PASI-90 and PASI-100 Stratified by Receipt of Any Biologics for Psoriasis, NRI	(Full Analysis Set)
14.2.2.2.1	Summary of PASI by Visit: Actual Values, Percent Changes, Proportions of Subjects Achieving PASI-50, PASI-75, PASI-90 and PASI-100, Complete Case Analysis	(Per Protocol Set)
14.2.2.2.2	Summary of PASI by Visit: Actual Values, Percent Changes, Proportions of Subjects Achieving PASI-50, PASI-75, PASI-90 and PASI-100, LOCF	(Per Protocol Set)
14.2.2.2.3	Summary of PASI by Visit: Proportions of Subjects Achieving PASI-50, PASI-75, PASI-90 and PASI100, NRI	(Per Protocol Set)
14.2.3.1.1	Proportion of Subjects with an sPGA Score of 0 or 1 and a 2-Point Reduction from Baseline, Complete Case Analysis	(Full Analysis Set)
14.2.3.1.2	Proportion of Subjects with an sPGA Score of 0 or 1 and a 2-Point Reduction from Baseline, LOCF	(Full Analysis Set)
14.2.3.1.3	Proportion of Subjects with an sPGA Score of 0 or 1 and a 2-Point Reduction from Baseline, NRI	(Full Analysis Set)
14.2.3.2.1	Proportion of Subjects with an sPGA Score of 0 or 1 and a 2-Point Reduction from Baseline, Complete Case Analysis	(Per Protocol Set)
14.2.3.2.2	Proportion of Subjects with an sPGA Score of 0 or 1 and a 2-Point Reduction from Baseline, LOCF	(Per Protocol Set)

This document is confidential.

Table Number	Name	Analysis Set
14.2.3.2.3	Proportion of Subjects with an sPGA Score of 0 or 1 and a 2-Point Reduction from Baseline, NRI	(Per Protocol Set)
14.2.4.1.1	Summary of DLQI by Visit: Actual Values, Changes from Baseline, Proportion of Subjects with at Least a 5-Point Reduction from Baseline	(Full Analysis Set)
14.2.4.1.2	Summary of DLQI by Visit: Actual Values, Changes from Baseline, Proportion of Subjects with at Least a 5-Point Reduction from Baseline	(Per Protocol Set)
14.2.4.2	DLQI: MMRM for Changes	(Full Analysis Set)
14.2.5	PASI: MMRM for Percent Changes from Baseline, Complete Case Analysis	(Full Analysis Set)
14.2.6.1	BSA: Summary of Visit Values and Changes from Baseline by Visit	(Full Analysis Set)
14.2.6.2	BSA: MMRM for Changes	(Full Analysis Set)
14.2.7.1.1	NRS: Summary of Visit Values and Changes from Baseline by Visit	(Full Analysis Set)
14.2.7.1.2	NRS: Summary of Visit Values and Changes from Baseline by Visit	(Per Protocol Set)
14.2.7.2	NRS: MMRM for Changes	(Full Analysis Set)
14.2.8.1.1	Summary of Time to the First Response of PASI-50	(Full Analysis Set)
14.2.8.1.3	Cox Proportional Hazard Model for Time to the First Response of PASI-50	(Full Analysis Set)
14.2.8.2.1	Summary of Time to the First Response of PASI-75	(Full Analysis Set)
14.2.8.2.3	Cox Proportional Hazard Model for Time to the First Response of PASI-75	(Full Analysis Set)
CCI		
14.2.11.1	Summary of Trough Plasma Concentrations (<unit>) of ME3183 and CCI by Visit	(PK Analysis Set)
CCI		
14.3.1.1	Overall Summary of Adverse Events	(Safety Analysis Set)
14.3.1.2	Treatment-Emergent Adverse Events by System Organ Class and Preferred Term	(Safety Analysis Set)
14.3.1.3	Treatment-Emergent Adverse Events by System Organ Class, Preferred Term and Maximum Severity	(Safety Analysis Set)
14.3.1.4	Treatment-Emergent Adverse Events by System Organ Class, Preferred Term and Maximum Relationship	(Safety Analysis Set)
14.3.1.5	Treatment-related Treatment-Emergent Adverse Events by System Organ Class and Preferred Term	(Safety Analysis Set)
14.3.1.6	Serious Treatment-Emergent Adverse Events by System Organ Class and Preferred Term	(Safety Analysis Set)
14.3.1.7	Treatment-Emergent Adverse Events Leading to Permanent Discontinuation of Study Drug by System Organ Class and Preferred Term	(Safety Analysis Set)
14.3.1.8	Treatment-Emergent Adverse Events by Time of Onset, System Organ Class and Preferred Term	(Safety Analysis Set)

This document is confidential.

Table Number	Name	Analysis Set
14.3.2.1	Serious Treatment-Emergent Adverse Events, Listing	(Safety Analysis Set)
14.3.2.2	Treatment-Emergent Adverse Events Leading to permanent Discontinuation of Study Drug, Listing	(Safety Analysis Set)
14.3.4.1.1.1	Hematology and Coagulation: Summary by Visit and Change from Baseline	(Safety Analysis Set)
14.3.4.1.1.2	Hematology and Coagulation: Proportion of Abnormal Results by Study Visit	(Safety Analysis Set)
14.3.4.1.2.1	Blood Chemistry: Summary by Visit and Change from Baseline	(Safety Analysis Set)
14.3.4.1.2.2	Blood Chemistry: Proportion of Abnormal Results by Study Visit	(Safety Analysis Set)
14.3.4.1.3	Urinalysis: Proportion of Abnormal Results by Study Visit	(Safety Analysis Set)
14.3.4.2	Summary of Vital Signs by Visit and Change from Baseline	(Safety Analysis Set)
14.3.4.3.1	12-Lead ECG: Summary by Visit and Change from Baseline	(Safety Analysis Set)
14.3.4.3.2	12-Lead ECG: Summary of Overall ECG Interpretation by Visit	(Safety Analysis Set)
14.3.4.3.3	12-Lead ECG: Summary of Noteworthy Changes of QT/QTc Interval by Visit	(Safety Analysis Set)

This document is confidential.

## 19. Index of Figures

Figure Number	Name	Analysis Set
14.2.8.1.2	Reverse Kaplan-Meier Plot of Time to the First Response of PASI-50	(Full Analysis Set)
14.2.8.2.2	Reverse Kaplan-Meier Plot of Time to the First Response of PASI-75	(Full Analysis Set)
14.2.11.2	Linear Mean ( $\pm$ SD) Plasma Ctrough Concentrations (<unit>) of ME3183 and CCI	(PK Analysis Set)

This document is confidential.

## 20. Index of Listings

Listing Number	Name	Analysis Set
16.2.1.1	Subject Disposition	(Screened Set)
16.2.1.2	Screen Failures	(Screened Set)
16.2.2	Subjects with Any Protocol Deviations	(Screened Set)
16.2.3	Subjects Excluded from Analysis Sets	(Screened Set)
16.2.4.1	Demographics and Baseline Characteristics	(Full Analysis Set)
16.2.4.2	Baseline Disease Characteristics	(Full Analysis Set)
16.2.4.3	Medical History	(Full Analysis Set)
16.2.4.4.1	Prior and Concomitant Medications	(Full Analysis Set)
16.2.4.4.2	Prior and Concomitant Medical/Surgical Procedures	(Full Analysis Set)
16.2.4.4.3	Prior Systemic Treatment for Psoriasis	(Full Analysis Set)
16.2.5.1	Study Drug Administration	(Full Analysis Set)
16.2.5.2	Study Drug Compliance	(Full Analysis Set)
16.2.6.1	Psoriasis Area and Severity Index (PSAI)	(Full Analysis Set)
16.2.6.2	Static Physician's Global Assessment (sPGA)	(Full Analysis Set)
16.2.6.3	Dermatology Life Quality Index (DLQI)	(Full Analysis Set)
16.2.6.4	Body Surface Area (BSA)	(Full Analysis Set)
16.2.6.5	Numerical Rating Scale (NRS)	(Full Analysis Set)
16.2.7.1	Treatment-Emergent Adverse Events	(Full Analysis Set)
16.2.7.2	Non-Treatment-Emergent Adverse Events	(Full Analysis Set)
16.2.8.1.1	Laboratory Reference Ranges	
16.2.8.1.2	Hematology and Coagulation	(Full Analysis Set)
16.2.8.1.3	Blood Chemistry	(Full Analysis Set)
16.2.8.1.4	Urinalysis (Dipstick)	(Full Analysis Set)
16.2.8.2.1	Vital Signs	(Full Analysis Set)
16.2.8.2.2	Electrocardiogram (ECG)	(Full Analysis Set)
16.2.8.2.3	Physical Examination	(Full Analysis Set)
16.2.8.2.4	Serology at Screening	(Full Analysis Set)
16.2.8.2.5	Serum Pregnancy Test and FSH at Screening	(Full Analysis Set)
16.2.8.2.6	Urine Pregnancy Test	(Full Analysis Set)
16.2.8.2.7	Individual Ctrough Concentrations	(Full Analysis Set)
CCI		

This document is confidential.

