## 8. General Aspects for Statistical Analysis

### 8.1. General Methods

- Unless otherwise specified, summaries will be presented for each treatment group and overall.
- Continuous variables will be summarized using the number of subjects (N), mean, standard deviation (SD), median, minimum, and maximum. Categorical variables will be tabulated with the number and percentage of subjects for each category.
- All relevant subject data will be included in listings. All subject data will be included in listings. The listings will be generally sorted by treatment and subject identification (ID), unless otherwise specified.

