## 13. Safety

All safety analyses will be performed using the safety analysis set.

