### 13.1. Adverse Events

An AE is any symptom, physical sign, syndrome, or disease that either emerges during the study or, if present at Screening, worsens during the study, regardless of the suspected cause of the event. AEs will be collected from the time the subject signs the ICF through 4 weeks after the last dose of study drug.

AEs will be coded according to the MedDRA Version 24.1 or higher. Unless otherwise specified, AEs will be summarized by SOC and PT by treatment group and overall, with SOCs presented in the standard international order and PTs within SOCs presented in descending order of subject incidence.

Adverse events are summarized by subject incidence rates. In any tabulation, a subject contributes only once to the count for a given SOC or PT. If a subject experiences more than 1 occurrence of the same AE, the occurrence with the greatest severity and the closest association with the study drug will be used in the summary tables.

For the purposes of this study, any AEs classified as 'Unrelated' or 'Unlikely' will be considered as 'Not Related' and 'Possibly', 'Probably', or 'Definitely' as 'Related' to the study treatment. Missing relationship will be considered related to study product.

All AEs will be listed by subject, along with information regarding onset, duration, relationship and severity to study drug, seriousness, action taken with study drug, and outcome.

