## 13.2. Laboratory Evaluations

Laboratory tests include the following:

- Viral serology (HBV, HCV, and HIV)
- Hematology and coagulation
- Blood chemistry
- Urinalysis (Dipstick)
- Pregnancy tests (WOCBP only; serum or urine  $\beta$ -human chorionic gonadotropin)
- Serum follicle-stimulating hormone (FSH) (postmenopausal women only)

Summary statistics of actual values and changes from baseline will be provided for each laboratory parameters by treatment group at each study visit if the results of the laboratory are continuous. Frequencies tables, including numbers and percentages of subjects with normal and abnormal (low vs high), will be presented for laboratory parameters with categorical results by treatment group at each study visit. Shift tables will also be provided displaying the numbers and percentages of subjects with normal and abnormal results compared with the results at baseline.

Viral serology and pregnancy test results will be summarized in listings only. Subject data listings of all laboratory data will be provided.

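### Do the Full Analysis Set labels on the SAP's 11 by-subject safety listings call for a change to the plan?

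*SAP*

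**What the plan says.** Section 20 of the SAP labels every by-subject safety listing with the FAS. Two examples are "16.2.7.1 Treatment-Emergent Adverse Events (Full Analysis Set" and "16.2.8.2.3 Physical Examination (Full Analysis Set". The same label is on the listings of non-treatment-emergent events, hematology and coagulation, chemistry, urinalysis, vital signs, ECG, serology, serum pregnancy/FSH and urine pregnancy.

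The text of the SAP points elsewhere. Section 13 states "All safety analyses will be performed using the safety analysis set", and Section 6.3 says the same for safety endpoints. Section 6.4 assigns the FAS to efficacy. On listings, Section 8.1 says "All subject data will be included in listings", Section 13.1 says "All AEs will be listed by subject", and Section 13.2 says "Subject data listings of all laboratory data will be provided". Sections 13.3 and 13.5 ask for the same completeness for vital signs and physical examinations. Section 13.2 also says "Viral serology and pregnancy test results will be summarized in listings only".

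**The concern.** The two sets differ in two ways. The Safety Analysis Set (Section 6.3) needs randomization and one dose, and groups subjects by treatment received. The FAS (Section 6.4) also needs at least one evaluable post-baseline time point for the primary endpoint, and groups subjects as randomized.

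Read literally, the index therefore drops from the listings any dosed subject who left before an evaluable PASI. Early leavers are the subjects whose safety data a reader most wants to see line by line. Physical examination, viral serology and pregnancy results are presented only in listings, so for such a subject they would appear nowhere. A subject given the wrong kits could be listed under one arm and tabulated under another.

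There is a further point about timing. Section 13.1 says "AEs will be collected from the time the subject signs the ICF through 4 weeks after the last dose of study drug", so an event in a subject who was never dosed would fall in neither AE listing. The stake is whether the listings reconcile with the safety tables they support.

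**Working it through.** The SAP gives no figure to reproduce on this point. The check is a count of labels, a comparison of the two set definitions, and an account of what would be lost.

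**1. Listings index (Section 20, visible entries).** Screened Set 4; no set 1 (laboratory reference ranges); FAS 25; Safety Analysis Set 0.

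- FAS entries: 6 (16.2.4.x) + 2 (16.2.5.x) + 5 (16.2.6.x) + 2 (16.2.7.x) + 3 (16.2.8.1.2 to 16.2.8.1.4) + 7 (16.2.8.2.1 to 16.2.8.2.7) = 25.
- By-subject safety listings among them: 2 AE + 3 laboratory + 6 (vital signs, ECG, examination, serology, serum pregnancy/FSH, urine pregnancy) = 11. All 11 carry the FAS.

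**2. Tables index (Section 18, visible 14.3 entries).** 8 AE tables + 2 AE listings (14.3.2.1, 14.3.2.2) + 5 laboratory + 1 vital signs + 3 ECG = 19. All 19 carry the Safety Analysis Set.

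**3. Who could be affected.** Only a dosed subject with no evaluable post-baseline PASI. PASI is scheduled at Weeks 1, 2, 4, 8, 12 and 16 (6 visits) and again at Week 20; the FAS definition does not say whether Week 20 counts. Protocol Section 7.4 asks for the Visit 8 assessments, which include PASI, when a subject terminates early. Leaving treatment early is therefore not enough to leave the FAS.

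The documents give no rate for this. As an illustration, suppose all 125 planned subjects are dosed and take the SAP's 10% drop-out assumption:

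- If every drop-out left without a post-baseline PASI: 0.10 × 125 = 12.5 subjects. This is the ceiling under that assumption.
- At an assumed 2%: 0.02 × 125 = 2.5 expected, and P(at least one) = 1 − 0.98^125 = 0.92.
- If every drop-out has at least one PASI: 0.

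**4. What such a subject would lose under a literal reading.**

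| Data | Still shown | Absent |
|---|---|---|
| Serious TEAEs; TEAEs leading to discontinuation | AE tables; listings 14.3.2.1 and 14.3.2.2 | Repeat entry in 16.2.7.1 |
| Other TEAEs | Counted in the 14.3.1 tables | Line detail |
| Laboratory, vital signs, ECG | Summarized in the 14.3.4 tables | Individual values |
| Physical examination | Clinically significant findings, reported as AEs (Section 13.5) | Other findings |
| Serology, pregnancy tests | Pregnancies, reported separately (Protocol 12.6.6) | Test results |
| Identity and reason for exclusion | Listing 16.2.3, Screened Set | Nothing |

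**5. Effect on results.** The safety tables take their set from Sections 6.3 and 13 and from their own labels in Section 18. Changing a listing label adds rows to an appendix and leaves every numerator and denominator as it was.

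**The case for a change.** The best case for changing the plan is that the contradiction is printed in the SAP and cheap to correct. It cannot be dismissed by saying that listings are not analyses: the SAP puts its own AE listings 14.3.2.1 and 14.3.2.2 on the Safety Analysis Set, and the sentences asking for all data bind listings directly. The labels are not redacted, and the separate shells (Section 21) are not said to override them. The mismatch also reaches beyond the 11. Six more FAS listings have matching tables on the Safety Analysis Set (16.2.4.3, 16.2.4.4.1 to 16.2.4.4.3, 16.2.5.1, 16.2.5.2), and the trough-concentration listing 16.2.8.2.7 differs from Section 6.6. That makes 11 + 6 + 1 = 18 labels.

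All of that stands as a description of the index. The consequences are weaker. The arm mismatch after mis-dispensation is conjecture: Sections 8.1 and 16.2.5.3 order listings by treatment without saying whether randomized or received, and the shells are not available. The point about undosed subjects turns on how Section 13.1 is read: it sits under a section that restricts safety work to dosed subjects, and events before any dose bear on no treatment comparison.

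Nor is there one clean replacement label. The Safety Analysis Set would still leave out data collected before dosing in subjects never dosed, against Section 8.1. Moving the concentration listing to the PK set would drop subjects excluded under Section 6.6 for receiving more than one active drug.

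**Conclusion.** The inconsistency is confirmed: 11 of 11 by-subject safety listings carry the FAS label, while 19 of 19 visible safety outputs in Section 18 carry the Safety Analysis Set. It is a clerical slip in an index, and correcting it would change no estimate, bias, precision or conclusion. At most, some line-level detail would be missing for a number of subjects that the documents do not give and that may be zero. The most important events would still be listed, and the omitted subjects would still be identified.

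This rests on three assumptions. The safety tables follow Sections 6.3, 13 and 18 as written. The programmers resolve the conflict in favor of the text, where Sections 8.1, 13.1, 13.2, 13.3 and 13.5 all ask for complete data, rather than the index label. The redacted rows at the end of Section 20, which could not be counted, do not alter the picture. If a dosed subject does fall outside the FAS, listing 16.2.3 will show it and the missing lines can be produced from data already held. No change to the plan is needed.
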